In Session 1 (pre-medication baseline), we will collect baseline measures of smoking urge, withdrawal symptoms, mood, cognitive performance, a behavioral economics-based measure of cigarette demand and effects of smoking a cigarette on cigarette reward, satisfaction and mood. Next, participants will be randomized to VAR (1 mg twice daily for 3 weeks) or PLA, using urn randomization to stratify on gender and dependence. Participants will complete a week of medication use using the standard dose run-up (0.5 mg once daily on days 1-3, 0.5 mg twice daily on days 4-7, then 1 mg twice daily until the end of the medication period). In Session 2, which occurs after one week on medication, participants will complete the same laboratory assessments as in Session 1. Next, participants will undergo a 3-day abstinence period. They will come to the laboratory twice per day and will receive escalating cash incentives for breath carbon monoxide (CO)-verified abstinence. At each visit, cigarette craving and withdrawal symptoms will be measured. At Session 8 (Thursday morning), participants who have been continuously abstinent will complete the same procedure as in Sessions 1. For ethical reasons, participants who complete the study through Thursday and who wish to remain abstinent may opt out of smoking during this session and will still receive full compensation for participation, as long as they attend this lab session and complete the other session measures.

Participants will be asked to return to the laboratory on Friday morning. Breath CO will be measured and time of first lapse (single cigarette) and relapse (return to regular smoking) will be collected among those who have lapsed and relapsed. Those still abstinent ($CO \leq 4$ ppm) since Session 8 will receive a small cash incentive. Next, participants will be shown how to use breath CO monitors with smart phones to record

and text us videos of themselves providing CO samples twice per day for the following week to determine time to lapse and relapse. Participants will receive \$5 for each submitted sample (not contingent on CO level), paid when the smart phone and CO monitor are returned at the end of the week.

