A total of 48 randomized participants are planned for the R21 phase. This sample size is based on Aim 1, which is to determine effects of VAR versus PLA on smoking urges and negative affect during abstinence, reinforcing effects of a smoking lapse, cognitive function and time to relapse in SS. A repeated-measures design with 48 total participants provides 80% power to detect main and interaction effects on the primary targets (smoking urges and negative affect during abstinence) and secondary targets (reinforcing effects of a smoking lapse) of at least $d = .40$ in size, assuming a moderate within-subject autocorrelation. While this effect size is somewhat smaller than those detected by West et al. (2008) for effects of abstinence on urges and negative affect during abstinence and smoking satisfaction and reward from relapse (d 's = .32-.44), abstinence was not controlled or biochemically verified after target quit date in that study, and, as the authors noted, it is possible that the effects that they observed were due only to those who were completely abstinent. With our rigorous control of abstinence, which includes twice-daily CO testing and a stringent abstinence criterion, we believe that we will detect smaller effects. We are not determining sample size based on Aim 2 (which is to examine the extent to which the effects of VAR on time to relapse are mediated through its effects on the target mechanisms), but we should be able to

detect medium-sized group effects on latency to second lapse, and estimate the size of mediation relationships that would be detectable as significant. We anticipate 20% attrition between enrollment and randomization. Therefore, we anticipate needing to enroll up to 60 participants (30 per group) to include 48 in the intent-to-treat sample.

R33 phase:

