All data will be collected for research purposes only. All forms will be marked with only subject ID, session number and date. All records will be stored in locked files (physical or on computer) in locked rooms accessible only to research staff. Data gathered from people who attend the screening but do not meet inclusion criteria or decide not to participate will be stripped of personal identifiers or links and only the reason for study exclusion will be kept.

Personal information (participant name, address, telephone number, email address, locator contact information) must be collected so that the research assistant can contact people to schedule assessments, call with session reminders and arrange transportation to sessions. These data will be stored in a locked file that does not contain ID code numbers. All other data will be stored in files locked in a separate location with only code numbers identifying subjects and no personal identifiers. A cross-index of code numbers and participant names will be kept in a separate, password-protected computer file that is available only to research staff, PI, and mandated agencies during audits (e.g., study sponsor and Brown University IRB).

Saliva specimens for cotinine analysis will be marked with a study ID number, stored in the locked laboratory suite, and sent to a commercial laboratory for analysis. We will track samples sent and analysis results received using a form stored on a password-protected computer.

Data Analysis Plan

R21 phase

Variables will be examined for distributional assumptions associated with analyses to be used and transformed if necessary. Groups will be compared on demographic and other individual difference measures using t-tests for continuous measures and chi-square tests for categorical measures. Analyses of the effects of Group (VAR, PLA) and Time (Sessions 2-8) on QSU and MNWS-negative affect scores will be conducted using generalized estimating equation (GEE) models (Zeger et al., 1988), which allow for varying numbers of observations per participant (to minimize bias due to attrition) while controlling for autocorrelation (AR1 structure). GEE will also be used to analyze the effects of Group and Time (Screening, Sessions 2 and 8) on BPRS and other psychiatric symptom scores. Mixed 2 x 2 Analysis of Variance tests (ANOVAs) will be used to examine effects of Group and Abstinence (Sessions 1 and 8) on CEQ scale scores,

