cognitive measure scores (with baseline scores covaried), CPT demand indices and within-session changes (post- minus pre-smoking) in CO level and positive and negative mood scale scores. Significant interactions will be followed by simple effects tests. Those who opt not to smoke in Session 8 will not be included in the Group x Abstinence analyses of CEQ, or pre-to-post smoking changes in CO or mood, but will be included in all other analyses (only one SS opted not to smoke in Session 8 in our previous study, Tidey et al., 2014). Latency to relapse will be defined as hours between the start of Session 8 and time of relapse, collected in person at Friday's session and by videoed CO sample in the follow-up week. We will follow up for one week after Friday's session, which is 8 days after Session 8. Thus, the maximum latency until second lapse will be 192 h, at which point data will be censored. Lapse latencies will be compared in VAR vs. PLA using a t-test. We will examine whether gender and FTND score (≤ 5 vs. ≥ 6) moderate the effects of VAR by adding these factors (separately) to each model.

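### Free improvement: the R21 GEE models for QSU and MNWS negative affect leave out the Session 1 score, which is already collected before drug and could enter as one covariate

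*Combined protocol and SAP*

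**What the plan says.** The Data Analysis Plan (R21 phase) reads: "Analyses of the effects of Group (VAR, PLA) and Time (Sessions 2-8) on QSU and MNWS-negative affect scores will be conducted using" GEE, a method chosen "to minimize bias due to attrition) while controlling for autocorrelation (AR1 structure"). The model terms named are Group and Time. Gender and FTND are added later, separately, as moderators only.

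The description of the R21 procedures in the Summary of the Protocol states: "In Session 1 (pre-medication baseline), we will collect baseline measures of smoking urge, withdrawal symptoms, mood". Randomization comes after that session. The next laboratory assessment is already on treatment: "In Session 2, which occurs after one week on medication". Twice-daily visits follow, up to Session 8 on Thursday morning.

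Baseline is used elsewhere in the R21 plan. The 2 x 2 ANOVAs have Session 1 as a level of Abstinence, and one group of outcomes is listed as "cognitive measure scores (with baseline scores covaried"). The psychiatric symptom GEE models include Screening as a time point.

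The Power Calculation (R21 phase) says that 48 participants "provides 80% power to detect main and interaction effects on the primary targets" at d = .40, "assuming a moderate within-subject autocorrelation".

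**The concern.** QSU total and MNWS negative affect are the primary target measures, and the R21 sample size rests on Aim 1, which they serve. Their models contain no drug-free measurement. Session 2 cannot stand in for one, because a week of medication precedes it. A varenicline effect that is present by Session 2 and constant afterwards shows only in the Group main effect, and that comparison makes no use of what is known about each participant before drug.

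If people differ stably in urge and negative affect, part of the between-person variance in that comparison could be removed at almost no cost. Because Session 1 precedes randomization, adjusting for it cannot absorb a drug effect, and every randomized participant should have the score. What is at stake is precision for the Group effect. The planned test is not made invalid by leaving the covariate out.

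**Working it through.** **Inputs.** From the documents: 48 randomized; d = .40; 7 on-drug sessions (2-8); significance at .05. Assumed: 24 per arm, a two-sided test, unit variance at each session, a constant effect over Sessions 2-8, and all correlations, since the plan gives none.

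**Formulas.** The Group main effect is approximated by comparing arms on each person's mean of Sessions 2-8.
- V = variance of that mean (the average of the 7 x 7 correlation matrix); c = its covariance with Session 1; R2 = c²/V.
- Unadjusted: noncentrality .40/√(2V/24), t with 46 df.
- Adjusted: V is replaced by V(1 - R2)(45/44), t with 45 df. The factor 45/44 charges for chance baseline imbalance, so the variance falls only if R2 exceeds 1/45 = 2.2%.

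**The plan's 80%.** AR(1) with rho = .3 gives V = .240, noncentrality .40/√(2 x .240/24) = 2.83 and power .79 (.807 by the normal approximation). AR(1) with rho = .5 gives .63. The stated figure is therefore matched for the main effect if moderate means rho near .3. The document gives no number, so this neither confirms nor refutes it.

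**Spacing of Session 1.** Seven sessions ending on Thursday morning, at two a day, are half a day apart. A week before Session 2 is then 7 x 2 = 14 such lags. Under AR(1), the correlation of Session 1 with Session 2 is rho^14, which is practically zero for rho up to .7.

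**Example, equal correlation .5.** V = (1 + 6 x .5)/7 = .571; c = .5; R2 = .25/.571 = .4375. Adjusted variance = .571 x .5625 x 45/44 = .329. Noncentrality goes from 1.83 to 2.42, and power from .434 to .657.

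| Correlation assumption | R2 | Power for Group, without to with Session 1 |
|---|---|---|
| AR(1) .3, 14-lag gap | 0 | .790 to .781 |
| AR(1) .5, 14-lag gap | 0 | .633 to .623 |
| AR(1) .7, 14-lag gap | 0 | .470 to .461 |
| Equal .3 | 22% | .573 to .673 |
| Equal .5 | 44% | .434 to .657 |
| Stable share .2 + AR(1) .5, 14-lag gap | 8% | .501 to .526 |
| Stable share .5 + AR(1) .3, 14-lag gap | 40% | .406 to .596 |
| Later sessions .5, Session 1 with them .3 | 16% | .434 to .489 |

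In the stable-share rows the correlation is s + (1 - s) x rho^lag. These two rows are the ends of the range for s = .2 to .5 and rho = .3 to .5: gains of about 3 and 19 points.

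**Group x Time.** In 1,500 simulated trials the SD of the Group x linear-time estimate was .066 without and .064 with Session 1 (AR(1) .5, Session 1 one lag before Session 2), and .038 and .039 (equal correlation .5). For the Group main effect under equal correlation .5, the SD fell from .215 to .165.

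**The case against.** The strongest objection is that the covariate gains nothing in the setting closest to the plan. The plan names AR(1), and of the averaged-session settings tried, AR(1) near .3 is the one that matches 80%. With Session 1 a week earlier, the covariate there loses about 1 point. This stands. Placing Session 1 only one lag before Session 2 would show gains at rho = .5 and .7 (.633 to .649 and .470 to .539), but the visit schedule does not support that spacing. A real gain needs a stable between-person component. That is plausible for self-rated urge and mood, but it is not documented. AR(1) is named as the structure for the GEE; the documents do not show that the scores follow it.

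Three further points stand. Session 1 is taken before the abstinence period, which may lower its correlation with later sessions. The power statement covers interaction effects too, and those gain little. The cognitive-score precedent is weak, because Session 1 is already a factor level in that ANOVA and it is unclear which baseline is covaried.

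A reader might infer more than the documents support:
- That the planned Group comparison is biased for want of a baseline. Omitting a pre-randomization covariate does not bias it. Equally, the comparison should not be called unbiased without qualification: Session 8 is completed by continuously abstinent participants, so missing scores may depend on lapse, and the covariate does not address that.
- That the 80% claim is wrong, or that the covariate restores it. No correlation is stated, so neither follows.
- That the decision to proceed to the R33 phase is affected. It rests on a separate rule about the share of participants with a 20% reduction.

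**Conclusion.** The point holds as a free improvement. The R21 models for both primary targets leave out a pre-drug score that is already collected, and no other section brings it in. The possible benefit is confined to the precision of the Group main effect. It runs from a loss of about 1 power point under pure AR(1) decay, through about 3 to 19 points with a modest stable component, to 10 points (equal correlation .3) or 22 points (equal correlation .5). Where in that range this trial would fall cannot be told from the documents.

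The figures assume 24 per arm, complete data, a constant d = .40 and a simple mean over Sessions 2-8 in place of the fitted GEE. The case for acting is the asymmetry: a small, bounded loss against a possibly large gain. Covariates for the randomization strata, the coding of Time and small-sample variance corrections are separate, optional matters, and this conclusion does not depend on them.

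**What to change.** Add one sentence to the Data Analysis Plan (R21 phase), before unblinding: each GEE model for QSU total and MNWS negative affect includes the Session 1 score of the same scale as a single covariate. Session 1 should not become another level of Time, so that the Group comparison over Sessions 2-8 stays as planned.

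The cost is one coefficient per model (between-subject df from 46 to 45), or about 1 power point if Session 1 proves uninformative. No new data are needed. The 2 x 2 ANOVAs that already use Session 1 need no change for this point.

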Standard operating procedures and case report form templates will be developed to ensure that data are collected consistently during the study. Each visit will have a checklist of all measures that need to be obtained and the order in which these measures are to be administered. Once a participant has completed all study procedures and all open events have been closed, the PI will review the participant's binder and sign a form indicating study completion for that participant. Oversight of the study and adherence to protocol procedures will be conducted by the PI or another study staff member (e.g., post-doctoral fellow) who has been trained and is supervised by the PI.

VAR and matching PLA will be prepared by a pharmacist by compounding VAR tablets or placebo lactose powder to capsules that are identical in appearance. The standard VAR dosing will be used: 0.5 mg/day on days 1–3, 0.5 mg twice daily (morning, evening) on days 4–7, then 1 mg twice daily to the end of the medication period. VAR and PLA will be distributed in identical 7-day medication blister packs, marked with the participant’s study identification number and letter code.

A medication randomization table will be created by the PI. The Research Assistant will be provided with a copy that has letter codes (A, B, C, or D) instead of medication names. When the Research Assistant enrolls a participant, the Research Assistant will enter the participant’s name and ID number on a row the table, note the medication letter code for that row on the participant’s enrollment form, and take the medication pack with that letter code. The Research Assistant will then provide the Data Manager with a copy of the randomization table so that the data manager can update his records.

[name] will remain blind to medication condition during each phase (R21 phase, R33 phase). The Data Manager will break the blind for [name] at the end of each phase. The Data Manager will break the blind for the medical monitor ([name]) in case of adverse events requiring medical intervention.

Regulatory Issues

Reporting of SAEs

Serious events as defined in 21 CFR 312.32 will be reported to the Brown University IRB, the NIDA Project Officer, and the DSMB. The Brown University IRB requires that fatalities and all other SAEs related to the study products be reported within 5 days of receiving notice of the event. SAEs related to the study will be reported to NIDA within 72 hours.

Reporting of IRB actions to NIDA

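### R21 allocation is stratified on gender and dependence, but the between-subject Group tests adjust for neither, so power may be forgone; type I error is not inflated

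*Combined protocol and SAP*

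**What the plan says.** The Brief Description of Protocol states that R21 participants are randomised "using urn randomization to stratify on gender and dependence". It does not say how dependence is categorised for the urn.

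The Data Analysis Plan for the R21 phase then sets out the Group comparisons:

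- **Primary targets (QSU, MNWS-negative affect):** GEE with an AR1 structure, described as "Analyses of the effects of Group (VAR, PLA) and Time (Sessions 2-8) on QSU and MNWS-negative affect scores".
- **CEQ, cognitive and CPT measures, and within-session changes:** 2 x 2 mixed ANOVA with Group and Abstinence (Sessions 1 and 8). Baseline is a covariate for the cognitive scores only.
- **Latency to relapse, censored at 192 h:** "Lapse latencies will be compared in VAR vs. PLA using a t-test".

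Gender and FTND (≤ 5 vs. ≥ 6) come in afterwards, to see whether they "moderate the effects of VAR by adding these factors (separately) to each model". No planned analysis contains both factors as adjustment terms.

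**The concern.** When allocation is balanced on a factor that predicts the outcome, that factor contributes little or nothing to the difference between arms. If the model omits it, its variance stays in the error term. The reported standard error is then larger than the true sampling error of the Group difference, and the test rejects less often than it should.

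The tests exposed to this are the between-subject ones: the GEE Group main effect on the two primary targets, and the latency comparison. All of these are listed as primary outcomes. With 48 randomised participants there is little power to spare. The moderator models do not fill the gap. They take one factor at a time and answer a different question, and they are not named as the main test of Group.

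**Working it through.** **Inputs from the documents.** "A total of 48 randomized participants are planned for the R21 phase" and "we anticipate needing to enroll up to 60 participants (30 per group) to include 48 in the intent-to-treat sample" (Power Calculation and Sample Size). With the stated 20% attrition, 48 / (1 − 0.20) = 60, so the enrolment figure reproduces. Thirty per group enrolled implies 1:1 allocation, hence 24 per arm randomised. The significance level is .05, taken as two-sided because the plan does not say.

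**The plan's own power figure.** The stated 80% power at d = .40 can be neither confirmed nor refuted, because the within-subject correlation is called only moderate and the number of measurements is not given. For the Group main effect on the mean of seven sessions under AR(1), power is 80.7% at a correlation of .3 and 65.2% at .5. The check below does not depend on that figure.

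**Assumptions.** R² is the share of between-subject variance of the analysed quantity that gender and dependence explain together. The documents give no value, so a range is used. The effect is d = .50, the conventional medium size, because the plan expects to detect medium-sized group effects on latency. The outcome is treated as normal and uncensored.

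**Formulas under exact balance, in SD units.**

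- Reported SE, unadjusted: √(2/24) = 0.289.
- True SE: 0.289 × √(1 − R²).
- Ratio of the two: 1/√(1 − R²).
- Size of the unadjusted test: 2 × [1 − Φ(1.96/√(1 − R²))].

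**Worked case, R² = 20%.**

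- True SE = 0.289 × 0.894 = 0.258.
- Size = 2 × [1 − Φ(1.96/0.894)] = 2 × [1 − Φ(2.19)] = 2.8%.
- Unadjusted power: the critical difference is 2.013 × 0.289 = 0.581, and 1 − Φ((0.581 − 0.50)/0.258) ≈ 38%.
- Adjusted power: noncentrality 0.50/0.258 = 1.94 against t = 2.015 on 44 df gives about 47%.

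**Results (24 per arm; power at d = .50, simulated under balance within strata).**

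| Assumed R² | SE ratio | Size, exact balance | Size, one plausible urn | Power, unadjusted | Power, adjusted | Gain (points, rough) |
|---|---|---|---|---|---|---|
| 5% | 1.026 | 4.4% | not run | 39% | 41% | 1–2 |
| 10% | 1.054 | 3.9% | 4.4% | 39% | 43% | 3–4 |
| 20% | 1.118 | 2.8% | 3.6% | 38% | 47% | 8–9 |
| 30% | 1.195 | 1.9% | 3.2% | 37% | 52% | 13–15 |

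The adjusted model's size stayed at 4.9–5.0% in the balanced simulations. Under the urn, power at R² = 20% went from about 38% to 45%. The urn settings are assumed, since the plan does not give them; simulations of such urns differed by up to about 0.4 point in size.

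**Within-subject tests.** A gender or dependence effect that is constant over sessions cancels from the Session 1 to Session 8 change. The simulated SE ratio for Group x Abstinence was about 0.999 at every R², so there is nothing to gain there. The same cancellation applies to Group x Time.

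**Cost of two extra terms.** Residual df fall from 46 to 44, and the critical t rises from 2.013 to 2.015.

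**The case against.** The strongest reply is that nothing here makes the R21 analysis invalid, and that the benefit could be close to nil. Both parts have force. The documents give no evidence on how far gender or dependence predicts urges, negative affect or latency, and eligibility (at least 10 cigarettes a day, CO above 10 ppm) may narrow the range of dependence. At R² of 5% or less the SE is overstated by under 3% and the gain is one or two points. An urn balances only approximately, so the conservatism is milder than exact balance implies. The move to R33 rests on a rule about the size of target reductions in a share of the sample, not on these p-values.

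Some stronger readings are tempting but unsupported:

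- **That the plan ignores the factors.** It does not; each is added to every model, though separately and for moderation.
- **That every Group comparison suffers.** The interaction tests do not.
- **That confidence intervals are miscalibrated.** The R21 plan specifies none for Group differences. Its only stated 95% intervals are for indirect effects.
- **That adjustment is worth 1/(1 − R²) times the participants.** Under exact balance the unadjusted difference already has essentially the same true variance as the adjusted one; only its reported SE is too large.

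What remains is that no planned between-subject test of Group uses both stratification factors.

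**Conclusion.** The point holds as a missed precision gain, confined to the GEE Group main effect on QSU and MNWS-negative affect and to the latency comparison. Any error is in the conservative direction. The size depends wholly on an R² that the documents do not supply: negligible near 5%, and worth having at 20% or more. The power figures also assume d = .50, 24 per arm and a normal outcome. For latency, which is censored at 192 h, they are only a guide. Adjustment remains sensible if urn balance turns out imperfect, because it then corrects chance imbalance on the same factors. This is an inexpensive improvement to make before unblinding, not a validity defect.

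**What to change.** In the Data Analysis Plan, R21 phase:

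1. State that the main GEE model for QSU and MNWS-negative affect includes gender and dependence together as covariates, alongside Group and Time.
2. Replace the unadjusted t-test on latency with a model containing Group, gender and dependence, of a type suited to the censoring at 192 h.
3. Define dependence exactly as the urn uses it, and say whether that is the FTND ≤ 5 / ≥ 6 split of the moderator analysis.
4. Keep the separate moderator models, labelled secondary. The interaction tests need no change on this account.

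The allocation description should be reconciled at the same time. Quality Assurance says "A medication randomization table will be created by the PI" and has it used row by row, with no mention of strata, whereas the protocol description specifies a stratified urn. The covariates should match whichever procedure is actually run.

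The cost is two residual degrees of freedom and analysis-plan wording. Gender and FTND are already collected.

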Mediation of the relationship between group and lapse latency will be examined using an SPSS macro (Preacher & Hayes, 2004). Hypothesized mediators will include baseline Calgary scale, cognitive performance and Contemplation Ladder scores, Session 8 QSU and MNWS scores, Session 8 CPT and CEQ Reward and Satisfaction scores, and Session 8 cognitive performance scores. Simple mediator models will be used to investigate the direct effect of medication on relapse latency (c path) with no mediator in the equation, as well as the medication \rightarrow mediator path (a), the mediator \rightarrow latency path (b), and the effect of medication on latency with the mediator in the equation (c' path). The indirect effect of medication on latency via each mediator ($c - c'$) is equal to the product of the coefficients of the "a" and "b" paths (i.e., "ab"). If ab is not normally distributed, 10,000 bootstrap resamples will be used to obtain lower and upper 95% confidence intervals (CI) for each indirect effect (Preacher & Hayes, 2008). All variables will be standardized first so that path coefficients can be directly compared across variables with different metrics. In addition, step-wise regression will be used to examine whether screening BPRS scores (entered in Step 1) and Session 8 BPRS scores (Step 2) predict latency to relapse. The SPSS mainframe statistical package (SPSS, Inc., Chicago, IL) will be used for GEE, mediation and regression analyses. All other analyses will be conducted using SPSS Statistics Version 20 for Windows (IBM, Armonk, NY). Differences will be considered significant when $p \leq .05$.

R33 phase

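### R21 primary targets: the plan does not say which model result shows a VAR effect; if either Group or Group × Time is accepted, the false-positive rate per measure is up to about 10%, not 5%

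*Combined protocol and SAP*

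**What the plan says.** The Data Analysis Plan (R21 phase) describes the primary-target model as "Analyses of the effects of Group (VAR, PLA) and Time (Sessions 2-8) on QSU and MNWS-negative affect scores", fitted by GEE with an AR(1) working correlation. It does not write out a Group × Time term for this model and names no deciding effect or contrast.

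The Power Calculation and Sample Size section states "A total of 48 randomized participants are planned for the R21 phase" and that a repeated-measures design of this size gives "80% power to detect main and interaction effects on the primary targets" and on the secondary targets, "of at least $d = .40$ in size, assuming a moderate within-subject autocorrelation". An interaction on the primary targets is therefore treated as an effect of interest.

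After describing the 2 × 2 ANOVAs for the other outcomes, the Data Analysis Plan adds "Significant interactions will be followed by simple effects tests". The R21 part closes with a single threshold of p ≤ .05 for all differences, with no hierarchy and no adjustment.

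The Brief Description of Protocol places Session 2 after one week on medication and before the 3-day abstinence period, which has two laboratory visits a day and ends with Session 8 on Thursday morning. Aim 1 concerns urges and negative affect during abstinence.

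**The concern.** A model with Group and Time has two results that could be reported as an effect of VAR on urges: the Group effect, and a Group × Time interaction. They mean different things. The first is a difference sustained over sessions. The second may reflect a difference at only one or two sessions. Because the plan powers for both and ranks neither, the choice can be made after the data are seen, and the 5% error rate no longer describes the claim. This problem sits within each measure and would remain if only one measure were primary.

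There is also a mismatch with the aim. An average over Sessions 2-8 gives one-seventh of its weight to a session at which abstinence has not begun. A difference during abstinence is diluted in the Group effect and appears partly as Group × Time.

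**Working it through.** **Inputs.** From the documents: 48 randomized, d = .40, significance at .05, seven sessions, AR(1). Assumed: 24 per arm (30 per group are to be enrolled), two-sided tests, d in units of the single-session SD, complete data, and AR(1) correlation ρ of .3 to .7, because the plan says only that it is moderate.

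**1. The plan's own 80%.** The variance of a person's mean over m sessions, in single-session SD² units, is v = [m + 2 Σ (m − k) ρ^k] / m², summed over k = 1 to m − 1. The noncentrality is d / √(2v/24).
- m = 7, ρ = .3: v = 0.2403 and noncentrality = .40 / √(2 × 0.2403/24) = 2.83. Power is 80.7% by the normal approximation and 79% by the noncentral t with 46 df.
- ρ = .5: v = 0.3476, power 63% (t). ρ = .7: v = 0.5182, power 47% (t).

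The stated 80% is therefore reached for the all-session Group effect at ρ = .3. It cannot be reproduced uniquely, because ρ is not given.

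**2. Error rate if either result counts, one measure.**
- Two independent 5% tests: 1 − .95² = 9.75%. The upper bound for any dependence is .05 + .05 = 10%.
- Simulation with no drug effect (24 per arm, seven sessions, 20,000 trials per ρ; t-test on person means for Group, Hotelling T² with 6 df for Group × Time): Group alone 4.8-5.2%, interaction alone 4.9-5.1%, either 9.5-10.0%.
- If Time is linear and Group is coded as the difference at a reference session, the two tests correlate at .80, .76 and .69 in absolute value for ρ = .3, .5 and .7. The rate is then 7.8%, 8.0% and 8.4%.

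These tests have exact size. Unadjusted robust Wald tests with 24 per arm gave about 12% to 18%, but that is a separate small-sample problem and is not counted here.

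**3. Which sessions are abstinence sessions.** Two visits a day for three days is six visits. Counting back from Session 8 gives Sessions 3-8. Session 2 is outside.

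**4. Power of the Sessions 3-8 average at 5%.** The same formula with m = 6:
- ρ = .3: v = 0.2755, noncentrality 2.64, power 73%
- ρ = .5: v = 0.3906, noncentrality 2.22, power 58%
- ρ = .7: v = 0.5632, noncentrality 1.85, power 44%

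**5. Comparison of the three rules for a 0.4 SD effect** (at ρ = .3 / .5 / .7).

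| Rule | Error rate | Constant effect, Sessions 2-8 | Effect in Sessions 3-8 only |
|---|---|---|---|
| Group over Sessions 2-8 | 5% | 79 / 63 / 47% | 66 / 51 / 37% |
| Either Group or Group × Time | about 10% | 80 / 65 / 49% | 70 / 57 / 49% |
| Average over Sessions 3-8 | 5% | 73 / 58 / 44% | 73 / 58 / 44% |

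In the last column the all-session Group effect is diluted to .40 × 6/7 = .343.

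**The case against.** The strongest reply is that the plan nowhere says that either result suffices. That is correct. A reader might infer that the R21 error rate is in fact double the nominal one, but the documents do not support that. They leave the rule open, and the figure of about 10% applies only if either result is accepted.

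A reader might also infer that the plan prescribes session-by-session tests of VAR against PLA on the primary targets. The simple-effects sentence directly follows the ANOVA description and may govern only those analyses. The R33 part, by contrast, writes out its Group × Session interaction. The point here does not need that sentence, because the power statement alone makes an interaction on the primary targets an effect of interest.

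A third tempting reading is that the interaction brings false positives and almost no power. That holds at ρ = .3, but for an effect confined to abstinence it adds about 12 points at ρ = .7 (37% to 49%). An effect that emerges during abstinence is partly a Group × Time effect, so it is reasonable for the sponsor to want the interaction reported.

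Finally, this is a 48-person laboratory study, and progression to the R33 phase rests on a reduction of at least 20% in at least half the sample (Brief Description of Protocol; Plans for Interim Analysis of Efficacy Data). No p-value enters that rule, so nothing here implies a faulty go/no-go decision. But the sample size is based on Aim 1 with an 80% power claim, so the test to which that claim refers should be identifiable.

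**Conclusion.** The gap is real and worth closing. The R21 plan names no deciding result for QSU or MNWS negative affect, powers for two kinds of effect, and applies p ≤ .05 to each. If either Group or Group × Time is accepted, the false-positive rate per measure is up to about 10%, or about 8% under a reference-session coding. This assumes tests of exact size. Separately, the Group effect over Sessions 2-8 is not purely an effect during abstinence.

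What is at stake is how a VAR effect on a target is reported under Aim 1. The power figures assume a two-sided 5% test, 24 per arm, complete data, AR(1) and a 0.4 SD effect. Missing sessions would lower them. Having two primary measures is a further multiplicity question and is not part of this point.

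**What to change.** In the Data Analysis Plan (R21 phase), state that the deciding contrast for each of QSU and MNWS negative affect is the VAR-PLA difference averaged over the abstinence sessions (Sessions 3-8), estimated from the GEE, tested at 5% and reported with a 95% CI. Say explicitly that Session 2 is left out of this contrast. Report Group × Time and the session-level differences as supportive, with no claim of a VAR effect from them alone.

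In Power Calculation and Sample Size, recalculate power for that contrast and state the value of ρ. The existing 80% cannot simply be reattached to it: with 24 per arm and d = .40 it is about 73%, 58% and 44% at ρ = .3, .5 and .7.

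The cost is a change of wording plus a new power calculation, with no new data. If the effect is constant from Session 2, the contrast has about 3 to 6 points less power than the all-session Group test. If the effect emerges during abstinence, it has slightly more power than accepting either test at ρ = .3 and .5, and about 5 points less at ρ = .7, with half the error rate. If the sponsor prefers to let both results count, testing each at .025 keeps the rate at or below 5% (1 − .975² = 4.94% if independent).
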